Allogeneic HB-adMSCs to provide immune support against COVID-19.

- The patient develops a severe allergic reaction that occurs following investigational product administration.

A patient may voluntarily withdraw or be withdrawn from the study at any time for reasons including, but not limited to, the following:

- Patient withdrawal of consent: At any time, a patient's participation in the study may terminate at his/her request. The specific reason for patient withdrawal will be noted on the case report form (CRF).
- Lost to follow-up: The patient stops coming for visits, and study personnel is unable to contact the patient after repeated attempts (e.g., mail, or email).
- This study may be terminated at the discretion of the Sponsor or any regulatory agency.

If a patient's infusions are discontinued at any point during the trial and the patient maintains consent to contribute additional outcome information, the patient should continue to be followed through Week 26 for all safety and efficacy assessments. Investigators will be trained about the importance of retention and steps to prevent missing data.

The date and reason for withdrawal are to be documented in the CRF. The study site must immediately notify the medical monitor. The patients who withdraw prematurely must attend an early discontinuation visit if possible, at which time they will complete all assessments described in Table 2 under the Week 24 visit.

In the event that a patient discontinues prematurely from the study due to an Adverse Event (AE) or serious AE, the event will be followed until it resolves (returns to normal or baseline values) or stabilizes, or until it is judged by the Investigator to be no longer clinically significant. Once a patient is withdrawn from the study, the patient may not re-enter the study. If the subject develops symptoms associated with COVID-19 during the conduct of this study, they will be asked to consult their personal physician and be tested for COVID-19, and to self-quarantine for at least 14 days. Quarantine must occur while waiting for COVID-19 test results. Once asymptomatic, subject may resume site visits. If the test results are positive, the subject will be asked to quarantine and may continue to receive infusions at the quarantine site. If the subject develops severe symptoms (i.e., shortness of breath/difficulty breathing) they should go to the ER instead of personal physician.

Treatments

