- Concomitant medications will be reviewed and updated if necessary.
- Medical History will be reviewed and updated if necessary. If the patient reported a medication which does not match the current medical history, further investigation will be required to determine whether it was an Adverse Event, or the patient just forgot to mention it before. If it is found to be an AE, it should be recorded in the appropriate CRF. If the patient forgot to mention it before, a note to file (NTF) should be made to clarify the case.
- Blood samples will be collected for laboratory assessments at weeks 0, 2, 6, 10, 14, and 26.

Allogeneic HB-adMSCs to provide immune support against COVID-19.

- Pre-infusion medications: Prior to IP administration the subject will be administered: Aspirin 81 mg per mouth, and Loratadine 10 mg per mouth
- Physical examination performed by principal investigator or sub-investigator.
- Patient will complete SF-36 and PHQ-9 assessments.
- Administer investigational product.
- Monitor for AEs. Observe the patient for at least 1 hour after infusion for symptoms of infusion-related reactions and allergic reactions, including anaphylaxis (See Appendix 1).
- Instruct the patient on recognition of delayed serious allergic reactions, including anaphylaxis and seeking for medical assistance.
- Telephone encounter 24 hours after the infusion will be performed to assess the occurrence of AEs.

Follow Up Weeks 18, and 22.

- Weight will be measured
- Vital Signs will be measured.
- Concomitant medications will be reviewed and updated if necessary.
- Medical History will be reviewed and updated if necessary. If the patient reported a medication which does not match the current medical history, further investigation will be required to determine whether it was an Adverse Event, or the patient just forgot to mention it before. If it is found to be an AE, it should be recorded in the appropriate CRF. If the patient forgot to mention it before, a note to file (NTF) should be made to clarify the case.
- Physical examination performed by principal investigator or sub-investigator.
- Patient will complete SF-36 and PHQ-9 assessments.
- Instruct the patient on recognition of delayed serious allergic reactions, including anaphylaxis and seeking for medical assistance.
- Telephone encounter 24 hours after the infusion will be performed to assess the occurrence of AEs.

Weeks 26 (End of the Study or Early Discontinuation Visit)

- Weight will be measured

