- Vital Signs will be measured.
- Concomitant medications will be reviewed and updated if necessary.
- Medical History will be reviewed and updated if necessary. If the patient reported a medication which does not match the current medical history, further investigation will be required to determine whether it was an Adverse Event, or the patient just forgot to mention it before. If it is found to be an AE, it should be recorded in the appropriate CRF.

Allogeneic HB-adMSCs to provide immune support against COVID-19.

If the patient forgot to mention it before, a note to file (NTF) should be made to clarify the case.

- Blood samples will be collected.
- Physical examination performed by principal investigator or sub-investigator
- Patient will complete SF-36 and PHQ-9 assessments.

If a patient prematurely withdraws from the study for any reason, the early discontinuation visit requirements should be completed. If the early discontinuation visit is not done, the reason(s) will be recorded in the CRF.

Unscheduled Visits

The Investigator may at his/her discretion arrange for a patient to have an unscheduled assessment, especially in the case of adverse events (AEs) that require follow-up, or an AE considered by the Investigator to be possibly related to the use of the investigational product. The unscheduled visit page in the CRF must be completed.

Efficacy Assessments

Complete Blood Count with Differential

The evaluation of the Complete Blood count with differential will help suspect the presence of a bacterial or viral infection with the predominance of either the neutrophils or lymphocytes. Generally, a healthy person's blood count would not show out of range values in the differential in the absence of a pathological condition.

CRP

C-reactive protein is considered to be an "acute phase protein," an early indicator of infectious or inflammatory conditions. CRP must be interpreted in the clinical context; no single value will be used to rule in or rule out a specific diagnosis.

SF-36

The Short Form (36) Health Survey is a 36-item, patient-reported survey of patient health. The SF-36 consists of eight scaled scores, which are the weighted sums of the questions in their section. Each scale is directly transformed into a 0-100 scale on the assumption that each question carries equal weight. The lower the score the more disability.

PHQ-9

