A complete physical examination (head, eyes, ears, nose, throat, heart, lungs, abdomen, skin, cervical and axillary lymph nodes, neurological, and musculoskeletal systems) will be performed

Allogeneic HB-adMSCs to provide immune support against COVID-19.

at baseline visit. In addition, medical history (including smoking history) will be recorded at baseline.

A limited physical examination to verify continued patient eligibility and to follow up any change in medical history will be performed at the visits indicated in the schedule of assessments. Symptom-driven physical examinations will be performed as clinically indicated at any study visit. All changes not present at baseline or described in the past medical history and identified as clinically noteworthy will be recorded as AEs.

Clinical Laboratory Parameters

The Investigator must review all laboratory reports and document the review. Any laboratory test result or change considered by the Investigator to be clinically significant should be considered an AE and recorded in the AE CRF. Clinically significant abnormal values occurring during the study will be followed until repeat test results return to normal, stabilize, or are no longer clinically significant.

Laboratory tests to be performed during the study:

Complete Blood Count with Differential	IL-6
Chemistry	IL-10
Coagulation study (PTT/PT/INR)	Tumor Necrosis Factor alpha
C Reactive Protein	Rapid Antibody Test for COVID-19

Adverse Events

An AE is any symptom, physical sign or disease that either emerges during the study or, if present at screening, worsens during the study, regardless of the suspected cause of the event. All medical and psychiatric conditions (except those related to the indication under study) present at screening will be documented in the medical history CRF. Changes in these conditions and new symptoms, physical signs, or diseases should be noted on the AE CRF during the rest of the study.

Clinically significant laboratory abnormalities should also be recorded as AEs. Surgical procedures that were planned before the patient enrolled in the study are not considered AEs if the conditions were known before study inclusion; the medical condition should be reported in the patient's medical history.

Serious Adverse Events (SAE)

A serious adverse event (SAE) is any AE that is:

Allogeneic HB-adMSCs to provide immune support against COVID-19.

- fatal
- life-threatening
- requires or prolongs hospital stay

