It is the responsibility of the Principal Investigator to oversee the safety of the study at his/her site. This safety monitoring will include careful assessment and appropriate reporting of adverse events as noted above. At Hope Biosciences, [name], MD [contact] will be responsible for reviewing any reported AEs and SAEs to determine if changes to the study need to be made or if the study should be stopped for the protection of patients. DSMB will review all deaths (to assure non-attribution), cases of anaphylaxis or suspected anaphylaxis, thromboembolic events, new malignancy/tumor, infections/hospitalizations (including unrelated to COVID-19 but due to underlying condition). After 15 subjects diagnosed with COVID-19, 5 subjects are hospitalized, or 3 subjects in the ICU, DSMB will review. DSMB will also review safety data at mid-point of the study.

Risks

Potential Risks of the Investigational Product and Clinical Investigation

Risks Associated with HB-adMSCs

Respiratory Risks:

A potential risk is that the infusion could initiate a VTE event with subsequent cardiopulmonary sequelae of respiratory failure and/or right heart strain/failure. We plan to monitor oxygen saturation, and respiratory rate/work of breathing for the first 2 hours post- infusion. The patient will be examined for VTE events (clinical exam, oxygen saturation) during each infusion visit and at each follow-up visit.

Hepatic Risks:

The reticuloendothelial system can sequester immature blood elements, theoretically resulting in hepatic injury. An acute elevation of the AST/ALT hepatic enzymes > 900 U/dl post-infusions will be considered an infusion related adverse event. This level is based upon the organ system scoring definitions for moderate hepatic failure and corresponds to the CTCAE v4.03 Grade 4 adverse event. It is unlikely that "end vessel" micro-thrombosis would occur in the liver due to the dual blood supply of the liver and the lung is the first pass organ. A CMP will be obtained at follow-up visits.

Coagulation Cascade:

A coagulation panel will be obtained at screening, baseline, infusion and the follow-up visits. The patient will be monitored for the development of venous thromboembolic events (see pulmonary monitoring above) as well as for the development of clinical deep vein thrombosis (limb swelling, tenderness, discoloration).

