8.2. Clinical Laboratory Analyses

Laboratory evaluations including the analyses of Biochemistry laboratory tests, Hematology laboratory tests and Coagulation tests (PTT/PT/INR). The details of the planned displays are in Appendix 5: List of Data Displays.

All laboratory parameters, including numerical urine analysis parameters will be summarised descriptively. Also, p-value for treatment difference using Analysis of variance (ANOVA) is displayed for lab parameters. Categorical urine analysis results will be summarized using count and percentage based on subjects.

Change from baseline will be summarised descriptively. Also, p-value for treatment difference using one-way Analysis of variance (ANOVA) is displayed for change from baseline.

Individual laboratory evaluations will be listed.

Data recorded at unscheduled assessments will not be included in tables and figures but will be listed.

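### SAP 8.2 keeps unscheduled laboratory results, which the protocol obtains chiefly to follow up adverse events, out of every by-arm laboratory summary

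*SAP*

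**What the plan says.** SAP 8.2 plans descriptive summaries of laboratory values and of change from baseline, with ANOVA p-values for treatment difference. It then adds: "Data recorded at unscheduled assessments will not be included in tables and figures but will be listed". It also says: "Individual laboratory evaluations will be listed". Details of the displays are deferred to Appendix 5, which is not in the supplied text.

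The protocol, under Unscheduled Visits, lets the Investigator "arrange for a patient to have an unscheduled assessment, especially in the case of adverse events (AEs) that require follow-up", or where an event may be related to the product. Under Clinical Laboratory Parameters, a result or change "considered by the Investigator to be clinically significant should be considered an AE and recorded in the AE CRF". SAP 8.1 tabulates adverse events by severity, relation, action and outcome, and by reported term. Clinically significant laboratory changes are a secondary endpoint in SAP 2.1. They do not appear in the secondary efficacy list in SAP 7.2.1, so 8.2 is where the values themselves are summarised.

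For patients who leave early, the protocol (Withdrawal, Removal, and Replacement of Patients) asks for an early discontinuation visit, "at which time they will complete all assessments described in Table 2 under the Week 24 visit". Table 2 has no such column. The protocol's Week 26 visit description covers end of study and early discontinuation together, and includes blood samples.

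**The concern.** Unscheduled draws are prompted by illness, so they are the draws most likely to contain an abnormal value. A rule that keeps them out of all laboratory tables and figures leaves by-arm summaries built only from planned time points, which will tend to look cleaner than the data collected. The adverse event tables count events by reported term. They do not show how high a value went or how far it moved from baseline, and entry depends on the Investigator judging the value clinically significant.

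This matters because the protocol names hepatic and coagulation harm as product risks, and describes the hepatic one as acute and post-infusion: "An acute elevation of the AST/ALT hepatic enzymes > 900 U/dl post-infusions will be considered an infusion related adverse event". A short-lived rise of that kind can easily fall between planned draws. A related gap is that the supplied SAP does not say how an early-discontinuation result is labelled. It could be shown as Week 26, as the nearest visit, as its own visit, or treated as unscheduled and left out.

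**Working it through.** The plan states no figure on this point, so there is nothing to reproduce. The check covers the text, then the scale.

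**1. What the rule reaches.** The sentence stands in the laboratory section. SAP 8.1 (adverse events) and 8.3 (vital signs, physical examination) carry no such rule. Within 8.2 it covers tables and figures without exception, so a shift or worst-value table in Appendix 5, if there is one, would also omit unscheduled values.

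**2. Which draws are scheduled.** The protocol gives three answers:
- Table 2: Weeks 0, 6, 14, 26.
- Infusion Visits text: Weeks 0, 2, 6, 10, 14, 26.
- Risks: a coagulation panel at screening, baseline, infusion and follow-up visits (post-baseline Weeks 2, 6, 10, 14, 18, 22, 26), and a CMP at follow-up visits.

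Until these agree, it is unclear whether, for example, a Week 10 result is scheduled.

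**3. Gap from each infusion to the next later draw** (assuming that draws at infusion visits precede dosing):

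| Infusion week | Next draw, Table 2 | Gap (weeks) | Next draw, Infusion Visits text | Gap (weeks) |
|---|---|---|---|---|
| 0 | 6 | 6 | 2 | 2 |
| 2 | 6 | 4 | 6 | 4 |
| 6 | 14 | 8 | 10 | 4 |
| 10 | 14 | 4 | 14 | 4 |
| 14 | 26 | 12 | 26 | 12 |

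Visit windows of ±4 days at both ends shorten a 4-week gap to 28 − 8 = 20 days at most. A two-week abnormality that starts at an infusion is therefore over before the next draw after all five infusions on Table 2, and after at least four of five on the text schedule.

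**4. Overlap under uniform onset.** Assume onset is uniform over 26 weeks and duration is D weeks. The documents give no duration, so D runs from 1 to 4. An abnormality is seen at a draw in week t if it starts in [t − D, t]. The share seen is the length of the union of these intervals, cut at Week 0, divided by 26.

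| D | Table 2 | Infusion Visits text | Coagulation, Risks text |
|---|---|---|---|
| 1 | 3/26 = 12% | 5/26 = 19% | 7/26 = 27% |
| 2 | 6/26 = 23% | 10/26 = 38% | 14/26 = 54% |
| 3 | 9/26 = 35% | 14/26 = 54% | 20/26 = 77% |
| 4 | 12/26 = 46% | 18/26 = 69% | 26/26 = 100% |

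(In the last two columns the Week 2 draw can contribute at most 2 weeks.)

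The remainder is seen off schedule, if at all.

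**5. Early discontinuation.** The Table 2 columns are Weeks 0, 2, 6, 10, 14, 18, 22 and 26. Week 24 is day 168. The Table 2 windows are days 151–157 for Week 22 and 179–185 for Week 26, so it fits neither. The two neighbours differ: Week 22 has no bloods, while Week 26 has bloods and the antibody test. For scale, the synopsis assumes 15% drop-out: 0.15 × 53 = 7.95, about 8 patients, or about 2 per arm if the four arms are equal (53/4 = 13.25).

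**The case against.** Much can be said for the plan, and several stronger readings fail.

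- **A reader might infer that the values disappear.** They do not. They are listed. Clinically significant ones are recorded and tabulated as adverse events, and the protocol makes the hepatic elevation it describes an adverse event in its own right. With about 13 patients per arm, listings can be read in full.
- **A reader might infer that patients who stop treatment drop out of the laboratory tables.** The protocol keeps patients who stop infusions but retain consent in follow-up through Week 26 for all assessments.
- **A reader might infer that early-discontinuation results fall under the exclusion, or that the Week 24 reference removes data.** The protocol defines that visit separately from unscheduled visits, and elsewhere pairs it with Week 26, bloods included. The reference is a contradiction to reconcile. By itself it deletes nothing.
- **A reader might take the overlap percentages as the share of data discarded.** They measure how sparse the planned sampling is. An abnormality that nobody samples is not excluded by the SAP.

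Keeping by-visit means and ANOVA on scheduled data is also sound, and Appendix 5 may already contain worst-value or shift tables.

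All of this stands. It does not answer the remaining point: adverse event counts by term do not give magnitude or shift, and the sentence in 8.2 as worded would keep unscheduled values out of any Appendix 5 laboratory table too.

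**Conclusion.** The point holds in a limited form. Followed as written, SAP 8.2 leaves the size and baseline shift of event-driven laboratory results out of every by-arm laboratory summary, although the results stay in listings and the clinically significant ones reach the adverse event tables.

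How much depends on off-schedule sampling is shown by the overlap with scheduled draws: 12% to 46% on Table 2, or 19% to 69% on the Infusion Visits draws. On the more frequent coagulation schedule in Risks the range is 27% to 100%, so the answer also turns on which schedule applies. These figures rest on uniform onset and an assumed duration of 1 to 4 weeks. The number of results actually excluded cannot be derived from the documents.

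The missing visit-assignment rule is a second, smaller gap. It concerns about 8 patients at the assumed drop-out rate, and fewer if some do not attend the visit. The correction should be made, but the documents do not support saying that safety data are lost.

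**What to change.** In the SAP:
- Keep the by-visit displays and ANOVA on scheduled data, and limit the exclusion sentence in 8.2 to those displays.
- Add, or confirm in Appendix 5, tables by arm of each patient's worst post-baseline value and shift from baseline for haematology, chemistry and coagulation. Use the Safety analysis set and all scheduled, unscheduled and early-discontinuation results.
- State a visit-assignment rule, with early-discontinuation results presented as their own visit and not as Week 26.

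In the protocol:
- Reconcile the Week 24 reference in the withdrawal section with Table 2 and with the Week 26 visit description.
- Reconcile the laboratory schedules in Table 2, the Infusion Visits text and the Risks section, so that it is clear which draws are scheduled.

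The cost is SAP wording, a few extra tables from data already collected, and protocol clarifications. The drawback is that a worst value depends partly on how often a patient was sampled, so the tables should be read with that in mind.

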8.3. Other Safety Analyses

The analyses of non-laboratory safety test results including physical examination and vital signs. The details of the planned displays are presented in Appendix 5: List of Data Displays.

Physical Examination and Vital signs will be summarized using count and percentage based on subjects. The vital signs based on visit and change from baseline will be summarized using descriptive statistics. Also, p-value for treatment difference using one-way Analysis of variance (ANOVA) is displayed for change from baseline.

Individual Vital signs, Physical Examination evaluations will be listed.

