2. SUMMARY OF KEY PROTOCOL INFORMATION

2.1. Study Objective(s) and Endpoint(s)

Objectives	Endpoints
Primary Objective	Primary Endpoint

 To investigate the efficacy of HB-adMSCs in providing immune support against development of Coronavirus Disease by incidence of hospitalization for COVID-19, incidence of symptoms associated with COVID-19 (ie., fever, shortness of breath/difficulty breathing, and/or cough), and severity of COVID-19 associated symptoms (fever 38C or higher, cough, shortness of breath/difficulty breathing). 	
 Incidence of hospitalization for COVID-19. Incidence of symptoms associated with COVID-19
Secondary Objectives	Secondary Endpoints

 To investigate the efficacy of HB-adMSCs in the prevention of upper and lower respiratory infections in a high-risk population. 	
 Absence of upper/lower respiratory infections (with hospitalization criteria) up to 3 months post infusions. Change from baseline in leukocyte differential Change from baseline in C-Reactive Protein Change from baseline in TNF-alpha Change from baseline in IL-6 Change from baseline in IL-10 Clinically significant changes in laboratory values, vital signs, weight and physical examination results. Incidence of AEs (AEs) and serious AEs (SAEs) related to the drug

Protocol Number: HBCOVID02
 Hope Biosciences
 Statistical Analysis Plan

Confidential

Date: 14-Oct-2021
 Version: 1.0
 Status: Final

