5.4 Multiple Comparisons and Multiplicity

The primary comparison of interest is the overall comparison between HB-adMSCs treatments and Placebo for the primary endpoint, incidence of the hospitalizations due to COVID-19 symptoms and incidence of the COVID-19 symptoms, so multiplicity adjustment is not needed. However, for exploratory purposes we perform a pair-wise comparison will done and results from following paired comparisons will be displayed to find the paired wise differences,

1. HB-adMSCs 200MM vs Placebo
2. HB-adMSCs 100MM vs Placebo
3. HB-adMSCs 50MM vs Placebo

We do statistical analysis for the primary endpoints and secondary outcomes as exploratory and test the outcome using $\alpha = 0.05$.

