5.5 General Considerations

Unless otherwise stated, all hypotheses will be tested at a 2-sided significance level of 0.05 and 95% confidence interval. All continuous measurements will be summarised descriptively at each visit by treatment using observed data.

Summary of continuous variables will be presented using N, Mean, Standard Error of mean (SE), Standard Deviation (SD), Median and Range (Minimum and Maximum). The categorical variables will be presented using number and percentage based on N.

For measurements over time mean values will be plotted to explore the trajectory over time. LOCF imputed data will be used as the basis for plotting data along with bars as standard error (SE) or Standard Deviation (SD), if not otherwise specified.

Primary endpoints of incidence of COVID-19 symptoms and Hospitalizations due to COVID-19 symptoms will be analysed based on binomial model and p-value will be displayed using two-sample binomial proportion test.

Additionally, time to first incidence of COVID-19 symptoms will analysed using Kaplan-Meir method.

A standard analysis of covariance (ANCOVA) model will be applied for secondary endpoints followed by Tukey's multiple comparison test to test the the significance of the effects of the treatment. The model includes treatment as fixed factor and the corresponding baseline value as a covariate.

Tukey's multiple comparison tests will be tested as two-sided hypotheses at a 5% level of significance. Treatment differences will be confirmed and considered significant if p-value reported is < 0.05 .

Protocol Number: HBCOVID02
Hope Biosciences
Statistical Analysis Plan

Confidential

Date: 14-Oct-2021
Version: 1.0
Status: Final

Presentation of results from a statistical analysis will include the estimated mean treatment effects (Least Square Means (LSMeans)) for absolute values and change from baseline. For all endpoints analysed statistically, estimated mean treatment differences will be presented together with two-sided 95% confidence intervals and p-values obtained using Tukey's method, and results from following paired comparisons will be displayed,

1. HB-adMSCs 200MM vs Placebo
2. HB-adMSCs 100MM vs Placebo
3. HB-adMSCs 50MM vs Placebo

All safety evaluations will be presented using Safety Analysis Set. The efficacy analysis will be presented using Efficacy analysis set.

Individual safety and efficacy parameters will be listed.

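### SAP 8.2 and 8.3 display unadjusted four-arm ANOVA p-values for laboratory values and vital signs without saying how to read them; estimates against placebo, labelled descriptive, would serve better

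*SAP*

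**What the plan says.** SAP 8.2 summarises laboratory parameters descriptively and adds that a "p-value for treatment difference using Analysis of variance (ANOVA) is displayed for lab parameters". It then gives a second ANOVA p-value for their change from baseline. SAP 8.3 does this for vital signs, for change only: a "p-value for treatment difference using one-way Analysis of variance (ANOVA) is displayed for change from baseline". Adverse events (SAP 8.1) and physical examination get no p-value.

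Three other parts of the SAP bear on how these p-values would be read:

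- SAP 5.5 sets the default: "Unless otherwise stated, all hypotheses will be tested at a 2-sided significance level of 0.05". Section 8 states nothing different.
- SAP 5.4 concludes for the primary comparison, "so multiplicity adjustment is not needed", and then says "We do statistical analysis for the primary endpoints and secondary outcomes as exploratory", with testing at 0.05. It has no sentence on safety analyses.
- SAP 2.1 lists as a secondary endpoint "Clinically significant changes in laboratory values, vital signs, weight and physical examination results".

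On timing, SAP 5.5 says "All continuous measurements will be summarised descriptively at each visit by treatment using observed data", and 8.3 summarises vital signs by visit. Neither section says in words that the p-value is repeated at each visit.

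**The concern.** A reader of the safety tables will meet many p-values on the usual 0.05 scale, with no statement that they are descriptive. Two misreadings follow. Some parameters will probably fall below 0.05 by chance and be taken as treatment effects. Others will lie above 0.05 and be taken as evidence of no difference, although the arms are too small for that.

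The second misreading matters here because the protocol (Statistical Analysis) frames its alternative safety hypothesis as the absence of drug-related harm, including harmful changes in laboratory values and vital signs. A non-significant ANOVA cannot support such a statement.

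The test is also uninformative in form. It compares four arms at once, so it does not identify the dose, the direction or the size of a difference, which is what a three-dose safety comparison needs. Nor does it address the listed endpoint: a comparison of arm means is not a count of patients with clinically significant changes.

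**Working it through.** The documents give no error rate, effect size, SD or test count for safety, so there is no planned figure to reproduce.

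**Inputs from the documents**
- Test level 0.05 (SAP 5.5).
- Five vital signs (Protocol, Vital Signs, Height, and Weight): temperature, pulse, oxygen saturation, systolic and diastolic pressure.
- Seven post-baseline visits with vital signs (Protocol Table 2): Weeks 2, 6, 10, 14, 18, 22 and 26.
- Three post-baseline laboratory visits in Table 2: Weeks 6, 14 and 26. The Infusion Visits text lists five post-baseline weeks, and the two passages must be reconciled. The lower count is used.
- 53 patients in four arms, taken as 13/13/13/14. The synopsis also gives 25 per group, which would be 100 in total; this too must be reconciled.
- 15% drop-out (synopsis): 53 × 0.85 ≈ 45, taken as 11/11/11/12.

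**Assumptions**
- P-values are given at each visit.
- Where laboratory tests are counted, 10 to 40 numeric analytes.
- For power, a shift in one dose arm only, in SD units.

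**Chance findings, vital signs**
- Tests: 5 × 7 = 35. Expected below 0.05 under no effect: 35 × 0.05 = 1.75.
- At least one, if independent: 1 − 0.95^35 = 0.83.
- Repeated measures are correlated, so null four-arm ANOVAs were simulated. The probability of at least one result below 0.05 was 0.74 with correlation 0.5 between visits only. It was 0.68, 0.62 and 0.49 for correlations between parameters/between visits of 0.2/0.6, 0.3/0.7 and 0.5/0.8. The expected number stays at about 1.75 throughout; correlation only clusters the chance results.

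**Chance findings, laboratory (analyte count assumed)**
- 20 analytes × 3 visits = 60 change tests, 60 × 0.05 = 3.0 expected. At least one: 0.90, 0.85 and 0.69 for the same three correlation pairs.
- 30 analytes × 3 = 90 tests, 4.5 expected. At least one: 0.96, 0.92 and 0.79.
- The p-values for absolute values come on top.

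**If only one visit carries a p-value**
- Five vital signs: 1 − 0.95^5 = 0.23.
- Six variables (weight counted) plus 10 to 40 analytes, change only, independent: 1 − 0.95^16 = 0.56 to 1 − 0.95^46 = 0.91.

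**Power of the four-arm F-test**

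With one arm of size n shifted by d SD, the noncentrality is λ = n·d²·(1 − n/N), referred to F with 3 and N − 4 degrees of freedom.

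| Shift | N = 53 | Power | N = 45 | Power |
|---|---|---|---|---|
| 0.5 SD | λ = 13 × 0.25 × 40/53 = 2.45 | 21% | λ = 11 × 0.25 × 34/45 = 2.08 | 18% |
| 0.8 SD | λ = 13 × 0.64 × 40/53 = 6.28 | 50% | λ = 11 × 0.64 × 34/45 = 5.32 | 43% |

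Power of 80% needs a shift of about 1.10 SD at N = 53 and 1.20 SD at N = 45. A two-sample t-test of one dose against placebo has 24% and 52% power for 0.5 and 0.8 SD at N = 53, so the limit is arm size and not the choice of ANOVA.

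**The case against.** The strongest reply is that only a label is missing. SAP 5.4 calls secondary outcomes exploratory, and laboratory and vital-sign changes appear in the secondary list. The p-values are merely displayed, and no decision depends on them; safety action runs through the stopping rules and the DSMB. Means and SDs by arm are already summarised, so direction and size can be seen. SAP 5.5 also promises treatment differences with 95% intervals for every endpoint analysed statistically. Finally, three intervals per parameter and visit turn 35 vital-sign tests into 35 × 3 = 105 nominal comparisons.

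Much of this stands. The exploratory sentence softens the problem, although the same sentence keeps the 0.05 level. The absence of a decision rule limits the harm to interpretation. Appendix 5, which lists the displays, is not in the supplied text, so table footnotes cannot be checked. The interval rule in 5.5 does not clearly supply the remedy: it is tied to p-values from Tukey's method, while section 8 names its own ANOVA. The extra intervals are a real cost, acceptable only if they are not read as tests.

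A reader might infer three stronger things that the documents do not support:
- That the secondary safety endpoint itself is near-certain to give false positives. The listed endpoint is clinically significant change, which these ANOVAs do not test; and near-certainty needs both by-visit p-values and an assumed analyte count.
- That a promised 5% overall error rate is breached. SAP 5.5 sets a level per test, and no familywise rate is stated for safety.
- That the ANOVA causes the low power. A pairwise test shares it.

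**Conclusion.** The point holds as a cheap improvement to the SAP, not as a flaw in a formal test. Sections 8.2 and 8.3 attach unadjusted omnibus p-values to many safety variables without a rule for reading them. If given at each visit, chance results below 0.05 are to be expected in the vital-sign tables alone: 1.75 on average, with a 50% to 83% probability of at least one. Laboratory tables raise this by an amount that rests on an assumed analyte count. In the other direction, a shift of 0.8 SD in one dose arm is missed about half the time, so p > 0.05 is weak evidence of no difference. The by-visit reading is an inference from SAP 5.5 and 8.3; with one visit only, the vital-sign figure falls to 23%.

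**What to change.** 1. In SAP 8.2 and 8.3, replace the ANOVA p-values with the mean difference of each dose minus placebo and a nominal 95% confidence interval, for each parameter at each scheduled visit. Label them descriptive, not adjusted for multiplicity, with no claim of significance. If the p-values are kept, print them under the same label.
2. In SAP 5.5, state that the 0.05 default does not apply to section 8.
3. For the listed secondary endpoint, tabulate the number and percentage of patients with clinically significant changes in each arm.

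Strict adjustment is not proposed. Bonferroni over 132 tests (30 assumed analytes × 3 visits, plus six vital-sign variables including weight × 7 visits) would cut power for a 1 SD shift in one arm from 71% to 13%.

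The cost is a wording change, one changed column and one added count table; no new data are needed. The p-value is lost as a screening flag, and there are more nominal intervals, which must not be read as tests. Power stays as it is, but a wide interval shows the uncertainty that p > 0.05 hides.
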